1. Discharged from hospital

Sponsor: Imperial College London

Version 1.1 22-Aug-2023

- 2. In-hospital without Organ Support
- 3. In-ICU with Organ Support
- 4. Death (absorbing state i.e. cannot transition out of this state)

Using data from the VANISH and LeoPARDS trials (44, 47) we estimated the proportion in each clinical state on days 0, 7, 14, 28 and 90 days in the standard of care arm (Table 2).

Sponsor: Imperial College London

Version 1.1 22-Aug-2023

Table 2: The anticipated probability of each clinical state over the first 90 days in the standard of care arm

State	0	7	14	28	90
1 = Discharge	0.00	0.06	0.21	0.42	0.60
2 = Hospital without support	0.15	0.48	0.32	0.17	0.05
3 = ICU with support	0.85	0.41	0.29	0.14	0.05
4 = Death	0.00	0.05	0.18	0.27	0.30

Simulations then estimated power for the new treatment under five scenarios, under which mortality reduction in the treatment arm was always kept at 3%, whereas the proportion transitioning to a better (lower) clinical state changed in each scenario, as shown in Table 3. Data for each simulation was generated using a Markov transition model. First, at least two sets of State Transition Probabilities (STP) corresponding to each timepoint and each scenario were estimated, using iterative methods to minimise the difference between the target clinical state probabilities and those derived from the STPs. Then, for each set of STPs, random draws of a standard (0,1) uniform distribution for each individual and timepoint were mapped onto the discrete clinical states by partitioning the interval [0,1] into sub-intervals with widths corresponding to the STPs. These simulations were analysed using a mixed effects proportional odds model which included the discrete timepoints, binary treatment variable and interactions between them as fixed effects, and participant as a random effect. In total 300 simulations were analysed for each scenario. The power was calculated based on the proportion of simulations from a two-sided hypothesis where the 95% confidence interval excluded the value of no difference (i.e. OR = 1).

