#### Exploratory estimands: treatment combinations

Further estimands as set out in Supplementary Table D will enable exploration of the combined effect of the interventions compared to standard of care in the event that each intervention in isolation shows no benefit.

Analysis population: We will use an Intention to Treat principle. Analyses will include all randomised participants in the arm they are allocated to regardless of the intervention received or intervention discontinuation but will exclude participants who are lost to follow-up with no data on the primary outcome at day 90, as no multiple imputation will be performed for the primary analysis. It is anticipated that >98% of all patients will have primary outcome data at day 90 and therefore there will be no substantial violation of the Intention to Treat principle. We expect that in this analysis population it will be possible to account for all participants' clinical status over time for the study

Sponsor: Imperial College London

Version 1.1 22-Aug-2023

duration up to day 90, and reasonable to assume discharged status if no mortality or inpatient record can be identified via data linkage; therefore no missing primary outcome data is expected.

**Analysis model:** A single factorial model will be used to simultaneously estimate the estimands for the diagnostic and fluid interventions in the full study population, and will also include GM-CSF treatment status as a covariate, as this approach results in unbiased marginal odds ratios for the primary estimands.(49) A second factorial model, using data only for the subjects eligible for GM-CSF, will be used to estimate the estimands for the GM-CSF trial, and will include the other interventions as covariates.

In both cases, in order to estimate the difference due to the intervention effect over time we will fit a longitudinal Proportional Odds model. This will provide the between arm proportional Odds Ratio of moving from one clinical state to a better clinical state averaged over the 90 days follow-up period. We will also use the models to estimate the between-arm proportional Odds Ratio of moving to a better clinical state on Day 90, and the 90-day mortality Odds Ratio between intervention arms. Terms for interactions between timepoints and treatment will be included. The models will have a random intercept for each subject and will adjust for covariates including age and the variables used for minimisation.

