### Sensitivity analysis to Primary analysis

A sensitivity analysis will replace the factorial models with multiarm models, in which the assumption of no interaction between treatments is relaxed.(49)

Further sensitivity analyses may explore alternatives to the proportional odds model (such as the Generalized Ordered Logit/Partial Proportional Odds Model or multinomial logistic regression) for the primary outcome.

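### The primary model gives each timepoint one shift common to all cut-points, which the plan's own Table 2 rules out, so a constant treatment effect is fitted as one that grows with time

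*Protocol*

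**What the plan says.** Under Analysis model in section 9, the primary analysis is fixed by the sentence "in order to estimate the difference due to the intervention effect over time we will fit a longitudinal Proportional Odds model". It adds "Terms for interactions between timepoints and treatment will be included" and "The models will have a random intercept for each subject and will adjust for covariates including age and the variables used for minimisation". The main output is a between-arm odds ratio averaged over follow-up. A Day 90 odds ratio ("We will also use the models to estimate the between-arm proportional Odds Ratio of moving to a better clinical state on Day 90") and a 90-day mortality odds ratio are to come from the same models.

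That paragraph does not say how time enters the cut-points. The only description is under Sample Size and power considerations, where the simulated trials were analysed with a "mixed effects proportional odds model which included the discrete timepoints, binary treatment variable and interactions between them as fixed effects". In a proportional odds model this gives each timepoint a single shift, shared by every cut-point.

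Table 2 in the same section sets out "The anticipated probability of each clinical state over the first 90 days in the standard of care arm". Its discharge row reads "1 = Discharge 0.00 0.06 0.21 0.42 0.60" for days 0, 7, 14, 28 and 90, and its death row runs 0.00, 0.05, 0.18, 0.27, 0.30.

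On relaxing proportionality, the section on sensitivity analyses says only: "Further sensitivity analyses may explore alternatives to the proportional odds model".

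**The concern.** Patients start in the two middle states and leave to both ends of the scale, discharge and death. Both probabilities rise over 90 days, so their cumulative logits move in opposite directions: the discharge cut-point goes towards better states and the survival cut-point towards worse ones. A single shift per timepoint cannot do both.

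The fault lies in the time effect, so it is present even when treatment acts exactly proportionally on every day. The model settles on one compromise spacing of the cut-points. That spacing is too narrow for day 7 and too wide for day 90, so the same treatment effect reads as small early and larger late. At stake are the apparent timing of benefit, the Day 90 OR and the model-based mortality OR.

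**Working it through.** **1. The plan's own figure.** With 30% against 25% mortality, two-sided 5% error and 90% power, n per arm = [1.960·√(2·0.275·0.725) + 1.2816·√(0.30·0.70 + 0.25·0.75)]² / 0.05² = 1674, as stated. Then 2 × 1674 × 1.10 / 0.98 = 3758, as stated. The Table 3 powers cannot be rebuilt, because the transition probabilities are not given. Nothing below depends on them.

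**2. Cumulative logits from Table 2 (control arm).**

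| Cut-point | Day 7 | Day 90 | Change |
|---|---|---|---|
| Discharged | logit 0.06 = −2.75 | logit 0.60 = +0.41 | +3.16 |
| Discharged or in hospital without support | logit 0.54 = +0.16 | logit 0.65 = +0.62 | +0.46 |
| Alive | logit 0.95 = +2.94 | logit 0.70 = +0.85 | −2.10 |

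The planned form needs these three changes to be equal. The outer cut-points are about 5.7 logits apart at day 7 and about 0.4 at day 90.

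**3. A constant effect.** Assume a treatment OR of 1.16 for a better state at every cut-point on days 7, 14, 28 and 90. At day 90 the odds of death become (0.30/0.70)/1.16 = 0.369, so mortality is 27%. This is the 3-point reduction used in the plan's simulations.

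**4. Planned form without a random intercept.** The model is logit P(state ≤ k at t) = θₖ + τₜ + βₜ·arm, fitted by maximum likelihood to the exact control and treated proportions (the large-sample limit). This needs only Table 2 and the assumed OR.

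| | Day 7 | Day 14 | Day 28 | Day 90 |
|---|---|---|---|---|
| True OR | 1.16 | 1.16 | 1.16 | 1.16 |
| Fitted OR | 1.07 | 1.13 | 1.21 | 1.25 |
| Fitted / true log OR | 0.43 | 0.83 | 1.28 | 1.48 |

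The equally weighted average is 1.16, which is right. A true OR of 1.22 gives 1.09, 1.18, 1.29 and 1.34. Adding day 0 at OR 1.16 gives 1.08, 1.16, 1.25 and 1.28 for the same four days.

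Fitted control mortality is 24% at day 7 (Table 2: 5%) and 11% at day 90 (Table 2: 30%). The model-based day-90 mortality OR is about 0.80, where the truth is 1/1.16 = 0.86. The implied mortality reduction is 1.9 points rather than 3.0.

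**5. With the random intercept.** This needs joint state sequences, which the protocol does not give. Three Markov chains were therefore assumed, each matched exactly to Table 2 with death absorbing, at a marginal OR of 1.16. The ORs below are conditional on the subject, so the columns are to be compared with each other and not with 1.16.

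| Chain | Common cut-points, days 7/14/28/90 | Log OR, day 90 ÷ day 7 | Cut-points free by timepoint |
|---|---|---|---|
| A | 1.15 / 1.28 / 1.37 / 1.42 | 2.58 | 1.38 / 1.39 / 1.40 / 1.39 |
| B | 1.17 / 1.32 / 1.43 / 1.48 | 2.46 | 1.23 / 1.24 / 1.23 / 1.21 |
| C | 1.11 / 1.21 / 1.30 / 1.33 | 2.81 | 1.26 / 1.27 / 1.28 / 1.28 |

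Data generated from a random-intercept model with constant conditional OR (subject SD 1, 2, 3) give fitted/true log-OR ratios rising from 0.43 to 1.36, 0.43 to 1.16 and 0.41 to 1.00 between day 7 and day 90. Free cut-points recover the true OR exactly on all four days.

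**6. Trials of the planned size.** In 120 simulated trials of 3758 patients (chain A, OR 1.16), the fitted day-90 OR exceeded the day-7 OR in 92%. A likelihood ratio test of time by treatment rejected in 43%. With no treatment effect it rejected in 12% and the fitted ORs stayed at 1.

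**The case against.** Common cut-points over time are partly inferred: Analysis model does not state the parameterisation, and the fixed-timepoint form comes from the power section. A statistical analysis plan is promised with all models and model checks, and the estimand section commits to a sensitivity analysis of statistical assumptions, so the optional one is not the only safeguard. These points stand. But the common-shift form is the natural reading and the only one described, and the plan's own figures already contradict it. Discovering the misfit at analysis is a poor substitute for specifying the model correctly.

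The main inference is barely touched. With a random intercept, at OR 1.22, the z statistics for the averaged effect under the two specifications are 3.60 and 3.59. This also stands, as does the fact that the protocol announces interaction terms but no interaction test, so the 43% describes how often a false trend would look convincing rather than the error of a planned test.

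A reader might infer that the averaged OR or the Day 90 OR is generally inflated. The documents do not support that. Without a random intercept the equally weighted average is right. With one, the average under common against free cut-points is 1.30 against 1.39 (chain A), 1.34 against 1.23 (B) and 1.23 against 1.27 (C): down, up, down. In a further assumed chain at OR 1.22, the day-90 value is 1.56 against 1.57. The direction depends on transition probabilities and subject variance that the protocol does not give. Nor does the model produce false positive findings of benefit.

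**Conclusion.** The point holds in a limited form. The single-shift time structure is incompatible with Table 2, which follows from arithmetic on the table alone. Two consequences are robust across everything tried.

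- A constant proportional effect is fitted as one that grows with time. Without a random intercept the fitted log OR goes from 0.43 to 1.48 times the truth. With one, under the three assumed chains, it grows about 2.5- to 2.8-fold.
- The fitted state probabilities are far from the data. With the random intercept, control mortality at day 90 is still fitted at about 12% against 30%.

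The timepoint-specific ORs and the model-based 90-day mortality OR are therefore unreliable. The averaged effect and its test are not shown to be seriously affected.

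This rests on the power-section form carrying over to the primary analysis, on an assumed constant OR (1.16; 1.22 gives nearly the same ratios), and, for the random-intercept results only, on assumed transition patterns.

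**What to change.** State under Analysis model that the cut-points differ by timepoint (or vary smoothly with day, if daily states are modelled), while treatment stays proportional within each timepoint. Apply this to both factorial models and to the Bayesian version, as the primary specification rather than an optional sensitivity analysis. Re-run the Table 3 simulations with it.

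For four timepoints the cost is 12 cut-points in place of 3 cut-points plus 3 time terms, and somewhat more demanding fitting. The z statistics above show no loss of power. The change removes the false trend but does not make a random-intercept model exact for Markov-type data. Under the three chains the implied day-90 mortality ORs after the change are 0.88, 0.95 and 0.86, against a true 0.86, so the simulations should also check how that OR is derived.

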# Design

Multicentre pragmatic randomised, multi-factorial, open-label trial with an embedded randomised double-blind, placebo-controlled, parallel group trial with internal pilot.

There will be up to three randomisations for each participant for the three trials i.e Diagnostic, Fluids or GM-CSF trial. In the first two, eligible patients with sepsis will be randomised on inclusion to

- (i) either PCR and procalcitonin guided antibiotic therapy or standard care in a 1:1 allocation ratio
- (ii) either a conservative fluid strategy with de-resuscitation or standard care in a 1:1 allocation ratio.

In the eligible subset of more severely ill patients (~35% of the total trial population) the third randomisation will allocate patients to the addition of GM-CSF or placebo in a 1:1 ratio.

Enrolment and allocation to treatment arms will be performed using an online system to ensure concealment. Treatment allocation will be by minimisation and will include a 20% random element.(41) The minimisation stratification variables will be:

- Diagnostic trial: Centre, vasopressor use (Y/N), source of infection (community vs hospital acquired)
- Fluid trial: Centre, respiratory support (Y/N), vasopressor use (Y/N)
- GM-CSF trial: Centre, allocation to Diagnostic and Fluid trials, source of infection (community vs hospital acquired)

We include an internal pilot study to assess adequate recruitment rates to each of the trials. The internal pilot will run for the initial 8 months of recruitment (~350 patients) and run seamlessly into the main trial, if the success criteria are met (see data analysis section for details). The internal pilot outcome and recruitment will be examined at 4 and 8 months. The 4-month look will allow for corrective action only.

The TSC will monitor recruitment and completion of follow-up to the primary outcome (day 90).

The TSC will also informally monitor measures of adherence:

- The median time to the PCR results being available in the intervention arm of the diagnostic trial
- The average separation in total fluid balance at day 3 in the fluid trial
- Adherence to IMP administration in the GM-CSF trial

Sponsor: Imperial College London

Version 1.1 22-Aug-2023

[figure not shown]

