#### 9. STATISTICAL ANALYSES

### Sample Size and power considerations

The sample size has been calculated based on 90-day mortality. To increase the power of the trial the primary outcome will include both 90-day mortality and clinical state (in-hospital without organ support, in-ICU with organ support, discharged) over 90 days. Simulations to further examine the power of the study under a range of conservative outcomes on the primary outcome with clinical state included have been performed on the planned trial sample size based on mortality alone.

The initial calculation used data from the ICNARC Case Mix Programme which reported a mortality rate of 31.8% for all sepsis admissions to ICU.(43) Allowing for the trial exclusion criteria we anticipate a 30% mortality rate in the standard of care arm.

In the diagnostic and fluid trials we aim to recruit 3758 patients to both trials. This is based on a clinically important target difference in mortality of 5%. Assuming 30% mortality, 5% reduction, 90% power, 5% two-sided type I error we will require 1674 per arm. We then inflate by 10% for a potential interaction effect between the intervention arms, and 2% to account for loss to follow-up.

The high-risk subset (35% eligibility for GM-CSF) will have a higher control mortality rate.(43-45) We assume a 45% mortality rate in the standard of care arm. Our meta-analysis for GM-CSF in sepsis trials demonstrated a relative risk for mortality of 0.74 (95%CI 0.49-1.14). We aim to recruit 1300 participants which will provide 90% power to detect 9% difference in mortality with type I two-sided error or 5%, and factoring in approximately 2% loss to follow up.

No adjustments for multiple comparisons have been made for these three trials as the comparisons are three distinct treatments where each result will provide a separate conclusion. (46)

In addition, we have undertaken simulations to further examine the power of the primary analysis of 90-day mortality and clinical states (in-hospital without organ support, in-hospital with organ support, discharged) for the antibiotic and fluid trials, assuming a more conservative reduction in mortality. Treating clinical state as an ordinal outcome which is repeatably observed over time increases statistical efficacy because it makes the most of all the information available. We define clinical status as an ordinal outcome with three passing states and one absorbing state.

Clinical status is categorised as:

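### The planned 90-day mortality odds ratio is the Day-90 proportional odds ratio inverted, and no committed analysis estimates 90-day mortality free of that assumption

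*Protocol*

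**What the plan says.** Protocol section 9, sample size: "The sample size has been calculated based on 90-day mortality". For the diagnostic and fluid trials: "Assuming 30% mortality, 5% reduction, 90% power, 5% two-sided type I error we will require 1674 per arm". For the GM-CSF trial: "We assume a 45% mortality rate in the standard of care arm" and "We aim to recruit 1300 participants which will provide 90% power to detect 9% difference in mortality".

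Protocol section 9, analysis model paragraph: the primary analysis is a longitudinal proportional odds model with a random intercept per participant, treatment-by-timepoint interactions, age and the minimisation variables. The same models are to give the Day-90 proportional odds ratio of "moving to a better clinical state on Day 90, and the 90-day mortality Odds Ratio between intervention arms". These are listed as two results. No treatment term specific to the death cut-point is stated.

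Protocol section 9, sensitivity analysis: "Further sensitivity analyses may explore alternatives to the proportional odds model". Generalised ordered logit, partial proportional odds and multinomial models are named there as possibilities.

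Protocol section 3, secondary endpoints: the list includes mortality at one year but not at 90 days.

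**The concern.** A proportional odds model has one treatment log odds ratio at each timepoint, shared by all three cut-points of the four-state scale: discharged versus the rest, out of organ support or discharged versus the rest, and alive versus dead. Treatment-by-time terms let that number change from day to day. They do not let it differ between death and discharge on the same day. The Day-90 odds ratio for death is therefore the reciprocal of the Day-90 odds ratio for a better state. Two labels are attached to one parameter, and that parameter is estimated from all the states.

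If treatment shifts discharge and death by different amounts on the log-odds scale, the figure labelled as mortality is wrong for mortality. A gain in discharge with no lives saved could be reported as a mortality benefit, or a real mortality benefit could be diluted. Readers of a trial sized on 90-day mortality will look for that number.

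**Working it through.** **1. The plan's own sample size.** Inputs are 30% versus 25%, two-sided 5%, 90% power and 1:1 allocation. The pooled-variance formula is

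n = [1.960 × √(2 × 0.275 × 0.725) + 1.282 × √(0.30 × 0.70 + 0.25 × 0.75)]² / 0.05² = 1673.9, so 1674 per arm.

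With the stated inflation ("We then inflate by 10% for a potential interaction effect between the intervention arms, and 2% to account for loss to follow-up"), 1674 × 2 × 1.1 / 0.98 = 3757.96, so 3758. Both figures reproduce. For the GM-CSF trial, 45% versus 36% needs 624 per arm, and 1248 / 0.98 = 1274, within the planned 1300. All three trials are thus sized on a binary comparison of deaths by Day 90.

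**2. What the ordinal model can say about death.** At Day 90 the model is logit P(state ≤ j) = a_j − b × treatment + (covariates, random intercept), for j = 1, 2, 3. The coefficient b has no index j. The odds ratio for death is exp(b) and the odds ratio for a better state is exp(−b).

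**3. Planning inputs at Day 90.** Protocol Table 2 gives the control arm as 0.60 discharged, 0.05 in hospital without support, 0.05 with support and 0.30 dead. The Table 3 changes sum to zero in each row, so I read them as percentage points. Mortality is 27% in the treated arm of every scenario:

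true mortality odds ratio = (0.27/0.73) / (0.30/0.70) = 0.863.

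**4. Cut-point odds ratios and the common fit.** The cut-point odds ratios (for a worse state) are the ratios of cumulative odds between arms. Scenario 1, for example, has treated proportions 0.61, 0.06, 0.06 and 0.27:
- not discharged: (0.39/0.61) / (0.40/0.60) = 0.959
- organ support or dead: (0.33/0.67) / (0.35/0.65) = 0.915
- dead: 0.863

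The common odds ratio is the large-sample maximum-likelihood fit of a proportional odds model to the two sets of Day-90 proportions.

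| Scenario | Cut-point odds ratios | Common odds ratio | Fitted mortality, control / treated | Implied reduction |
|---|---|---|---|---|
| 1 | 0.959, 0.915, 0.863 | 0.927 | 29.28% / 27.74% | 1.5 points |
| 2 | 0.959, 0.874, 0.863 | 0.924 | 29.32% / 27.70% | 1.6 points |
| 3 | 0.959, 0.834, 0.863 | 0.920 | 29.36% / 27.66% | 1.7 points |
| 4 | 0.881, 0.834, 0.863 | 0.872 | 29.90% / 27.11% | 2.8 points |
| 5 | 0.844, 0.796, 0.863 | 0.845 | 30.21% / 26.78% | 3.4 points |

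With 1879 per arm (3758 / 2), the 95% interval around the common odds ratio covers 0.863 about 80% to 83% of the time in scenarios 1 to 3, and about 94% to 95% in scenarios 4 and 5.

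**5. Mortality unchanged.** Move 1.5 points from each in-hospital state to discharge, so the treated arm is 0.63, 0.035, 0.035 and 0.30. The true mortality odds ratio is 1.00 and the common odds ratio is 0.918.

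**6. A separate dead/alive comparison.** It returns 0.863 in every scenario and 1.00 in step 5. With 1879 per arm the standard error of its log odds ratio is √[(1/0.30 + 1/0.70 + 1/0.27 + 1/0.73) / 1879] = 0.072, against about 0.065 for the common odds ratio.

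**The case against.** The strongest reply has four parts.

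First, the mortality odds ratio is an additional output. The primary estimands in Appendix 2 are summarised by the odds ratio across four states, and sizing on mortality while analysing an ordinal outcome that contains death is openly stated. This stands, and it limits the seriousness of the point. It does not make the additional output a mortality estimate.

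Second, the estimate is valid if proportional odds holds, and scenarios 4 and 5 nearly satisfy it at Day 90. This also stands. A reader might infer that the trial can never obtain a valid mortality estimate, or that every planning scenario materially breaches the assumption. The documents support neither. The material breach is in scenarios 1 to 3.

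Third, the statistical analysis plan is not shown and may add a mortality model, and the protocol already names partial proportional odds and multinomial models. But these are optional in the protocol, whose stated rule is that the mortality odds ratio comes from the proportional odds models. Deriving mortality from fitted state probabilities would still rest on the shared treatment coefficient.

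Fourth, step 4 is not the planned model. That is correct, and the figures are offered only as an illustration. A reader might want to take a Day-90 odds ratio from a random-intercept fit and apply it to 30% mortality to get a larger distortion. That mixes a subject-specific odds ratio with a population risk, and any such fit needs transition probabilities that the protocol does not give. I rely on no such figure.

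**Conclusion.** The point holds. As written, the protocol's 90-day mortality odds ratio is the Day-90 proportional odds ratio inverted, and nothing it commits to estimates 90-day mortality without the proportional odds assumption. That follows from the stated model terms and needs no numerical assumption.

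The size is illustrative. In a cross-sectional Day-90 fit to the protocol's own figures, a true 3-point reduction reads as 1.5 to 1.7 points in scenarios 1 to 3, is about right in scenarios 4 and 5, and a null mortality effect reads as 0.918 when 3 points move to discharge. This rests on Tables 2 and 3 being taken at face value and on Day 90 being analysed alone. The size, and possibly the direction, of the discrepancy in the longitudinal model cannot be fixed from the protocol.

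The validity of the primary ordinal analysis is not in question here.

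**What to change.** In the analysis model paragraph of section 9, replace the mortality odds ratio taken from the proportional odds models with one of the following, prespecified for each of the three trials:

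- a dead/alive analysis at Day 90: a logistic model with the same covariates as the primary model, reported as an odds ratio and a standardised risk difference, each with a 95% confidence interval; or
- a partial proportional odds model with a committed treatment effect specific to the death cut-point.

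The primary analysis stays as it is, and no new ranking of endpoints is needed.

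The cost is a wording change and one extra model per trial on data already collected. The mortality interval will usually be wider. At 1879 per arm an unadjusted dead/alive comparison has about 53% power for a 3-point reduction, though it has the stated 90% at 1674 per arm for the 5-point difference that sized the trial.

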Population-level summary measure	Odds Ratio from a proportional odds model across the 4 clinical states conditional on age and minimisation variables.	Odds Ratio from a proportional odds model across the 4 clinical states conditional on age and minimisation variables.	Odds Ratio from a proportional odds model across the 4 clinical states conditional on age and minimisation variables.
	Posterior Probability of being in a better clinical state using a Bayesian Proportional Odds model with vague priors.	Posterior Probability of being in a better clinical state using a Bayesian Proportional Odds model with vague priors.	Posterior Probability of being in a better clinical state using a Bayesian Proportional Odds model with vague priors.

Sponsor: Imperial College London

Version 1.1 22-Aug-2023

Rationale for the estimand	The aim of the trial is to assess whether the diagnostics intervention as given can improve on standard of care in the population of eligible patients.	result among the entire eligible population, it	the fluids intervention may potentially be adopted as standard of care.
----------------------------	---	---	---

<sup>1 A treatment policy strategy considers the occurrence of the associated intercurrent event as irrelevant, and participant data are analysed regardless.

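### The Day-90 odds ratio is taken from a random-intercept model that does not fit an absorbing death state: with model-based standard errors its interval is too narrow, and its scale is not that of the estimand tables

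*Protocol*

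**What the plan says.** Protocol section 9, Analysis model, fixes two factorial models, one for the diagnostic and fluid comparisons and one for GM-CSF. Both are longitudinal proportional odds models with timepoint-by-treatment interactions: "The models will have a random intercept for each subject and will adjust for covariates including age and the variables used for minimisation". The leading output is the odds ratio averaged over 90 days. The Day-90 odds ratio and the 90-day mortality odds ratio are also taken from these models.

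The sample size text in the same section lists four states, the last being "Death (absorbing state i.e. cannot transition out of this state". Of its power simulations it says: "Data for each simulation was generated using a Markov transition model". Those simulations were analysed with a participant random effect.

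Supplementary Tables A, B and C give the summary measure as "Odds Ratio from a proportional odds model across the 4 clinical states conditional on age and minimisation variables". No subject effect appears there. The listed sensitivity analyses relax the no-interaction and proportional odds assumptions. None concerns dependence between days.

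**The concern.** A random intercept makes any two days in the same patient equally correlated, given the covariates. These data do not behave that way. Death is permanent and discharge nearly so, so later states largely repeat one another while early states do not. When the assumed dependence is wrong in this way, the model-based standard error of a single-day contrast need not match its true sampling variability.

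There is also a question of scale. An odds ratio conditional on a subject effect lies further from 1 than one conditional on age and minimisation variables alone. The estimand tables describe the second; the model's coefficient is the first.

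The sample size rests on 90-day mortality, and Day-90 results are what clinicians are likely to read first. An interval that excludes 1 too often under no effect, on a scale that readers would not expect, could mislead them. The Bayesian margin for meaningful superiority would be hard to interpret if it were set on a different scale from the model's.

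**Working it through.** **1. The plan's own figure.** "Assuming 30% mortality, 5% reduction, 90% power, 5% two-sided type I error we will require 1674 per arm". With pooled variance and mean rate 0.275:

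n = [1.960·√(2·0.275·0.725) + 1.282·√(0.30·0.70 + 0.25·0.75)]² / 0.05² = (1.238 + 0.808)² / 0.0025 ≈ 1674 per arm.

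The protocol then says "We then inflate by 10% for a potential interaction effect between the intervention arms, and 2% to account for loss to follow-up": 1674 × 2 × 1.10 / 0.98 = 3757.96, so 3758, or 1879 per arm. The figure reproduces.

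**2. Inputs for the check.** Table 2 ("The anticipated probability of each clinical state over the first 90 days in the standard of care arm"), in the order discharged / hospital without support / ICU with support / dead:

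- Day 0: 0 / 0.15 / 0.85 / 0
- Day 7: 0.06 / 0.48 / 0.41 / 0.05
- Day 14: 0.21 / 0.32 / 0.29 / 0.18
- Day 28: 0.42 / 0.17 / 0.14 / 0.27
- Day 90: 0.60 / 0.05 / 0.05 / 0.30

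The transition probabilities are not published. They were assumed: several sets, with death absorbing, fitted to Table 2 by iterative proportional fitting.

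**3. Method.** With 1879 per arm and no effect, fit a proportional odds model with a subject random intercept and time-by-treatment terms by maximum likelihood. Let r = model-based SE / true SE. The interval is too narrow by 1 − r, and type I error ≈ 2[1 − Φ(1.96 r)]. For r = 0.76: 2[1 − Φ(1.49)] ≈ 0.136.

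**4. Day-90 contrast, no effect.**

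| Days entered as outcomes | r | Too narrow by | Type I error |
|---|---|---|---|
| 7, 14, 28, 90 (quadrature, sandwich as truth) | 0.76 | 24% | about 13.5% |
| Same, 600 simulated trials; high / medium / low persistence | 0.768 / 0.724 / 0.735 | 23% / 28% / 26% | 12.8% / 16.3% / 15.3% |
| 13 weekly visits | 0.88-0.89 | 11-12% | 8.2-8.5% |
| Daily to Day 28, plus Day 90 | 0.68 | 32% | 18-19% |
| Day 0 added, quadrature (r solved from type I error) | about 0.67 | about 33% | 18.6% |
| Day 0 added, simulated, no treatment effect on Day 0 | 0.578-0.623 | 38-42% | 23.2-27.3% |

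The Monte Carlo standard error at 5% with 600 runs is √(0.05·0.95/600) = 0.9 percentage points.

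**5. Checks that the model is the cause.**

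- On data that truly follow a random-intercept model, the fitter gave r = 0.975 and 5.0%.
- On the Markov data, a plain Day-90 proportional odds model gave 5.0-6.7%.
- In 400 simulated trials, the random-intercept fit rejected in 14.5% with model-based SEs and 4.0% with subject-level sandwich SEs.

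**6. Averaged odds ratio, no effect.** With post-baseline days only, r = 0.969 / 0.942 / 0.922 and type I error 5.8% / 6.5% / 7.0%; the quadrature calculation gave 5.3-6.8%. With Day 0 as an outcome row, r = 0.602 / 0.604 / 0.647 and 24.3% / 24.2% / 22.5%.

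**7. Scale.** Day-90 log odds ratios without Day 0, high / medium persistence:

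- Table 3 scenario 5: 0.474 / 0.433 with the subject effect, against 0.171 / 0.175 from a Day-90 model without it. As odds ratios this is about 1.54-1.61 against about 1.19; the log ratios differ by factors of 2.8 and 2.5.
- Scenario 1: 0.226 / 0.204 against 0.078 / 0.081, factors of 2.9 and 2.5.

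A separate calculation put the factor at 1.5-2.2, so the direction is firm and the size is not.

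**8. Table 3.** In scenario 5 (stated power 0.88) the random-intercept Day-90 contrast without Day 0 rejected in 0.89-0.90, and the plain Day-90 model in 0.72-0.75. The published powers cannot be reproduced exactly, because neither the transitions nor the tested contrast is given.

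**The case against.** **The lead measure is the averaged odds ratio.** This stands. The Day-90 and mortality odds ratios are additional outputs, no separate Day-90 test is defined, and interpretation is to rest on magnitude and precision. A reader might infer that the trial's main result has a badly inflated error rate. At about 5-7% it does not, unless Day 0 is modelled as an outcome. The protocol does not say that it is, and the visit schedule labels Day 0 as before randomisation.

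**No single percentage belongs to the protocol.** This also stands. Analysis days, standard-error method and transitions are not fixed, so 24% is one case within a range. The calculations omit age, minimisation variables, centre and the second factor.

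**Robust intervals could come in the analysis plan.** True: sandwich standard errors are compatible with the wording, so the error-rate point is conditional on model-based ones. They would not change the scale of the coefficient, and the random intercept is already fixed.

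**The word *marginal* in the Analysis model text is not a contradiction.** It occurs in a sentence about the factorial model and cites work on factorial estimands, so it plausibly means averaged over the other interventions. It should not be counted as a further, conflicting promise.

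**The odds ratio is not inflated.** Correct: odds ratios are non-collapsible, and a subject-specific one is a different measure, not a biased one. What remains is that the estimand tables describe a measure without the subject effect.

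**Conclusion.** The point holds for the Day-90 odds ratio, and for the mortality odds ratio if it is drawn from that contrast. Every transition set and visit grid tried gave a Day-90 interval that was too narrow with model-based standard errors: about 24% for days 7, 14, 28 and 90, from about 11% with weekly visits to about 42% with Day 0 as an outcome row. This rests on Table 2, no treatment effect, assumed transitions and no covariates.

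The mismatch of scale applies to every odds ratio read from the random-intercept coefficients. These should not be read as the ratio in Supplementary Tables A-C.

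Two further inferences are not supported. The first is that the Bayesian analysis is overconfident by the same amount: it would share the misspecification if it kept the random intercept, but this was not computed. The second is that the Table 3 powers are wrong: they used the same model class and deserve a re-check, but the published inputs do not allow a firm conclusion.

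**What to change.** In both factorial models:

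- Use subject-level sandwich or bootstrap confidence intervals.
- Obtain the Day-90 and mortality odds ratios from a Day-90 proportional odds or logistic model conditional on age and the minimisation variables, or by standardising the longitudinal model to a population-averaged odds ratio.
- State that Day 0 is not an outcome row.
- Say whether the averaged odds ratio is subject-specific or population-averaged, and align the Analysis model text with Supplementary Tables A-C.
- Set the Bayesian margin for meaningful superiority on that same scale.

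A proportional odds model conditional on the previous state is an optional alternative or sensitivity analysis. It would itself need standardising, because the estimand tables do not list previous state either. Replacing the whole primary model is not required.

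The cost is wording in the protocol and analysis plan, standard software, and a re-check of Table 3. The visible consequences are a wider Day-90 interval relative to its estimate and an odds ratio nearer 1. The change is best made before data extraction, since a later one could look data-driven.
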